1.4 CETUXIMAB

For full details on the background, clinical safety and efficacy of cetuximab in CRC refer to cetuximab Summary of Product Characteristics (SPC) ([79](#)).

1.5 RATIONALE FOR THE STUDY

As described in [Section 1.2](#) (Oncogenic BRAF Kinase Mutations in Various Cancers), mutations in the BRAF gene, in particular mutations resulting in a V600E mutant kinase, may play significant roles in the pathogenesis of a variety of clinically significant cancers. Moreover, the presence of BRAF mutations is known to attenuate the activity of other anticancer agents, most notably EGFR therapeutic antibodies. Therefore, the identification of new therapies that specifically target BRAF mutations in cancer cells is of significant interest.

Vemurafenib has reproducibly demonstrated high anticancer activity in a number of phase I, II and phase III trials in metastatic melanoma. Based on this prior activity, as well as the evidence that activated BRAF kinase may play a highly conserved role in dysregulated cell growth across multiple cancer types, it is reasonable to posit that this new drug may be effective in non-melanoma cancers harbouring BRAF V600 mutations, as well. Indeed, preliminary evidence suggested that vemurafenib may have some activity in CRC ([66](#)). This further encourages exploration of the efficacy of vemurafenib in CRC and other non-melanoma tumours harbouring activated BRAF V600 mutations.

As described in [Section 1.2.2](#) (Colorectal Cancer) there is preclinical evidence that BRAF inhibition causes a feedback activation of EGFR which is responsible for the continued proliferation in the presence of BRAF inhibition in CRC cell lines. The combination of vemurafenib and EGFR inhibitors demonstrated a strong synergic effect both *in vitro* and *in vivo*. These data provide a strong rationale for a clinical trial investigating the combination of vemurafenib and cetuximab in BRAF-mutated colorectal cancer patients, who have a poor clinical outcome and for whom there are no effective treatment options after failure of standard chemotherapy as per Cohort 3b.

2. OBJECTIVES

2.1 PRIMARY OBJECTIVE

The primary objective of this trial is to evaluate the efficacy of vemurafenib in patients with cancers harbouring BRAF V600 mutations as response rate (RR) at Week 8 determined by the Investigator using Response Evaluation Criteria In Solid Tumors, Version 1.1 (RECIST, v1.1)* or International Myeloma Working Group (IMWG) uniform response criteria and to identify tumour types for further development

*For prostate cancer, ECD and/or LCH specific response criteria see [Appendix 9](#) and [Appendix 10](#), respectively.

2.2 SECONDARY OBJECTIVES

- To evaluate the safety and tolerability of vemurafenib in this patient population.
- To evaluate in solid tumours and multiple myeloma (MM):
 - overall response rate (ORR)
 - clinical benefit rate (CR [or sCR], PR [or VGPR] and stable disease [SD]) of vemurafenib
 - duration of response (DOR)
 - time to response
 - time to tumour progression (TPP)
 - PFS
 - overall survival (OS)
- To determine the maximum tolerated dose (MTD) and recommended dose for stage I/II of the combination of vemurafenib and cetuximab in BRAF V600-positive metastatic CRC patients (Cohort 3b only)
- To investigate the safety, tolerability, efficacy of the combination of vemurafenib and cetuximab in BRAF V600-positive metastatic CRC patients (Cohort 3b only)
- To evaluate tumour assessment scans by an IRC for Cohort 1 (NSCLC) and other cohorts that demonstrate clinically meaningful efficacy per investigator assessment.

2.3 EXPLORATORY OBJECTIVES

- To perform concordance testing for the detection of BRAF V600 mutation in tumour samples via either the Roche CoDx cobas 4800 BRAF V600 Test or other standard methodology.

- To examine the previous line of treatment's TTP (pITT) in relation to the TTP achieved during study treatment
- For all newly enrolled patients in all cohorts:
 - To explore the PK characteristics of vemurafenib
 - To assess the correlation of BRAF V600 mutation between tissue samples and plasma samples

3. STUDY DESIGN

3.1 OVERVIEW OF STUDY DESIGN

[figure not shown]
This is an open-label, multicentre, multinational, phase II study exploring the efficacy and safety of vemurafenib in a diverse population of patients with cancers (excluding melanoma and papillary thyroid cancer) known to harbour BRAF V600 mutations and for whom vemurafenib is deemed the best treatment option in the opinion of the Investigator.

In the population of colorectal cancer patients, the safety and efficacy of vemurafenib in combination with cetuximab will also be explored in addition to vemurafenib monotherapy.

Patients with BRAF V600 mutation-positive cancers will be identified through mutation analysis assays as routinely performed at each participating site according to their local procedure. The BRAF V600 mutation identified at the site, as well as the specific BRAF mutation assay that was performed, will be recorded in the electronic case report form (eCRF). The presence of BRAF V600 mutations will be retrospectively confirmed by the Roche CoDx cobas 4800 BRAF V600 Test or other standard methodology.

The trial will consist of a Screening Period (Day -28 to -1), a Treatment Period, an End of Treatment Visit occurring when study medication is discontinued for any reason, a Safety Follow-Up Visit occurring 28 days (\pm 5 days) after the last dose of study medication and a Survival Follow-Up Period lasting for a minimum of 12 months after the last patient has been enrolled or until all patients have died, withdrawn consent or are lost to follow-up (whichever occurs first) to monitor survival status. Day 1 of the study (baseline) will be defined as the first day a patient receives study medication. One cycle of therapy will be defined as 28 days of treatment. Patients will be asked to attend clinic visits at regular intervals during the study for safety and efficacy assessments.

Figure 1: Study Design

The study will include 7 cohorts of patients with the following cancers:

- Cohort 1: Non-small cell lung cancer (NSCLC)
- Cohort 2: Ovarian cancer
- Cohort 3: Colorectal cancer
 - Cohort 3a: Vemurafenib only
 - Cohort 3b: Combination therapy with vemurafenib and cetuximab
- Cohort 4: Cholangiocarcinoma / cancer of the biliary tract
- Cohort 5: Breast cancer
- Cohort 6: Multiple myeloma (MM)
- Cohort 7: Solid tumours other than the above

Colorectal cancer patients with BRAF V600 mutation-positive cancers will receive vemurafenib as a single agent (Cohort 3a) or the combination of vemurafenib and cetuximab (Cohort 3b).

The Cohort 3b is designed to investigate the safety, tolerability, efficacy and to determine the MTD and the recommended dose for stage I/II of the combination of vemurafenib and cetuximab. Cohort 3b has two parts:

- Part 1 is a dose finding phase of vemurafenib in combination with cetuximab (based on a classical 3+3 design)
- Part 2 is investigating the efficacy and safety of the recommended dose for stage I/II of the combination of vemurafenib and cetuximab and will be the same Stage I/II design as the other cohorts will be used

The decision to carry on enrolment of CRC patients into Cohort 3a (vemurafenib monotherapy) and/or enrol patients into Cohort 3b (combination of vemurafenib and cetuximab) will be based on the stage I analysis for Cohort 3a (vemurafenib monotherapy). This will be decided by the Sponsor in discussion with study Steering Committee. The decision to continue enrolment in Cohort 3b after the Part I dose escalation phase will be decided by the Sponsor in discussion with study Steering Committee.

Recruitment/enrolment in any of the above cohorts may present some challenges due to the low frequency of BRAF V600 mutations in the specific disease settings. Therefore the following rule on cohort closure (permanent enrolment stop) will be applied: if no patients are enrolled in the remaining cohorts one year after any of the cohorts has completed enrolment, then enrolment in those remaining cohorts will be stopped. Cohort 7 (Other solid tumours) will be closed to enrolment when all other cohorts are closed, regardless of the number of patients recruited at that time. This cohort is quite heterogeneous and will be examined primarily to seek efficacy signals in the relatively rare BRAF V600 mutation-positive tumours.

Enrolled patients will receive:

- Cohorts 1 – 7 (except patients in the Cohort 3b): continuous oral dosing of vemurafenib at 960 mg twice daily (b.i.d)
- Cohort 3b: Part 1 vemurafenib and cetuximab at the doses allocated for dose escalation (see [Section 6.3.1](#)) or Part 2 at the dose recommended for stage I/II of vemurafenib and cetuximab

Treatment will continue until the development of progressive disease (as per Investigator assessment), unacceptable toxicity, withdrawal of consent, protocol violation endangering the patient's safety, death, reasons deemed critical by the treating physician, or study termination by the Sponsor.

Patients who develop disease progression but, in the opinion of the Investigator, would still benefit from continuing study treatment may continue treatment with study treatment after discussion with the Sponsor.

Patients with ECD/LCH have the option of discontinuing vemurafenib treatment after one year, if the investigator considers it to be in the best interest of the patient. Patients can then resume vemurafenib treatment if they become symptomatic or if their scans show worsening of their disease.

Recruitment into any cohort/indication can be expanded up to a total of 70 patients if a response rate has been demonstrated in Stage II of that cohort as per stopping rules defined in the protocol or a clear clinical benefit for patients is observed. This will be decided by the Sponsor in discussion with study Steering Committee.

Prior to the closure of the trial, the Sponsor may offer patients who have completed the protocol-mandated minimum 12-month safety follow-up and who continue to benefit from vemurafenib therapy, the opportunity to receive continued vemurafenib via enrolment in the GO28399 extension trial. Should the study be closed due to Sponsor decision, the Sponsor will offer all patients still receiving vemurafenib therapy the opportunity to receive continued treatment with vemurafenib via enrollment in the GO28399 extension trial at the time of study closure.

3.1.1 Rationale for Study Design

The multi-cohort design will allow for the examination of 7 separate cohorts of different cancers with enough statistical power to determine whether further examination may be warranted in the individual indications. The open-label, uncontrolled design is appropriate since the trial will only enrol patients with BRAF V600 mutation positive cancers, who in the opinion of the Investigator, have vemurafenib as their best treatment option, i.e., no other obvious comparator is available.

The Cohort 3b is designed to investigate the safety, tolerability, efficacy and determine the maximum tolerated dose (MTD) and recommended dose for stage I/II of the combination of vemurafenib and cetuximab in BRAF V600 positive CRC.

Recruitment into any cohort/indication can be expanded up to a total of 70 patients if a response rate has been demonstrated in Stage II of that cohort as per stopping rules defined in the protocol or a clear clinical benefit for patients is observed. This will be decided by the Sponsor in discussion with study Steering Committee. The data from these additional patients will help further characterize the safety and efficacy of vemurafenib in the specific indication.

3.1.2 Rationale for Dose Selection

3.1.2.1 Rationale for the starting doses of vemurafenib (Cohort 1-7, excluding Cohort 3b)

The dose of vemurafenib at 960 mg b.i.d was identified in the phase I dose-finding study PLX 06-02 and is established as the recommended dosage for phase II and III trials (see [Section 1.2.4](#)) for the treatment of melanoma. It is presumed that a similar dosage would be effective in other types of cancers harbouring the same BRAF V600 mutations.

3.1.2.2 Rationale for the starting doses of vemurafenib and cetuximab in combination (Cohort 3b)

The loading dose of cetuximab will be 300 mg/m² given intravenously (IV) followed by a weekly IV dose of 200 mg/m² (see [Appendix 1](#) for body surface area calculation). These doses are respectively 75% and 80% of the registered doses as single agent in second or third line for advanced CRC.

Vemurafenib: the starting dose will be 720 mg b.i.d. This is 75% of the registered dose in melanoma when given as single agent.

These starting reduced doses will be explored for safety reasons as vemurafenib and cetuximab will be administered concomitantly.

Doses will be escalated according to a standard 3+3 dose-escalation design (see [Section 6.3.1](#)).

3.1.3 End of Study

The end of study will occur when all patients have been followed for survival for a minimum period of 12 months after the last patient has been enrolled or until all patients have died, withdrawn consent or are lost to follow up, whichever occurs first.

At this time, the trial will end and no further data will be collected on the clinical database for this study. The end of the MO28072 study is defined as the last patient last visit at the end of the follow-up period.

Prior to the closure of the trial, the Sponsor may offer patients who have completed the protocol-mandated minimum 12-month safety follow-up and who continue to benefit from vemurafenib therapy, the opportunity to receive continued vemurafenib via enrolment in the GO28399 extension trial. Should the study be closed due to Sponsor decision, the Sponsor will offer all patients still receiving vemurafenib therapy the opportunity to receive continued treatment with vemurafenib via enrollment in the GO28399 extension trial at the time of study closure.

3.2 NUMBER OF PATIENTS / ASSIGNMENT TO TREATMENT GROUPS

It is estimated that up to 170 patients with solid tumours or multiple myeloma will be enrolled in this study for the Stage I/II analysis. Approximately 13–37 patients per indication (cohort) will be included. The number of patients in a cohort can be less than 13 if a cohort is closed earlier as a result of stopping rules for the cohort.

Recruitment into any cohort/indication can be expanded up to a total of 70 patients if a response rate has been demonstrated in Stage II of that cohort as per stopping rules defined in the protocol or a clear clinical benefit for patients is observed. This will be decided by the Sponsor in discussion with study Steering Committee. The maximum number of patients in this study is therefore 490 (7 cohorts up to 70 patients each).

3.3 CENTRES

This study is a multinational, multicentre study conducted in 6 countries and approximately 30 sites.

4. STUDY POPULATION

4.1 OVERVIEW

The target population will include adult patients with BRAF V600 mutation-positive cancers (excluding melanoma and papillary thyroid cancer). BRAF V600 mutations will be identified by mutation analysis assays as routinely performed at each individual participating site according to their local procedures. See [Sections 4.2 and 4.3](#) for further Inclusion and Exclusion Criteria.

4.2 INCLUSION CRITERIA

Inclusion Criteria:

For solid tumours only*

1. Histologically confirmed cancers (excluding melanoma and papillary thyroid cancer) that harbour a BRAF V600 mutation and are refractory to standard therapy or for which standard or curative therapy does not exist or is not considered appropriate by the Investigator

Note: for the patient to be eligible, they must be able to provide a tumour sample (preferably tissue; alternatively DNA) for retrospective confirmation of the BRAF mutation by a central laboratory. This tumour sample should preferably be from the original specimen used to detect the BRAF mutation. If archival samples are not available, the patient should be biopsied in order to obtain adequate tissue. Exceptions may be considered upon discussion with the Sponsor (e.g. ≥ 250 ng of DNA may be sent instead of tissue samples).

2. Measurable disease according to RECIST, v1.1
3. Adequate hematologic function, as defined by the following laboratory values; test performed within 7 days prior to the first dose of vemurafenib:
 - a. Absolute neutrophil count (ANC) $\geq 1.5 \times 10^9/L$
 - b. Platelet count $\geq 100 \times 10^9/L$

For multiple myeloma only:

4. Patients with a confirmed diagnosis of MM harbouring a BRAF V600 mutation

Note: for the patient to be eligible, they must be able to provide a tumour sample (preferably tissue; alternatively DNA) for retrospective confirmation of the BRAF mutation by a central laboratory. This tumour sample should preferably be from the original specimen used to detect the BRAF mutation. If archival samples are not available, the patient should be biopsied in order to obtain adequate tissue. Exceptions may be considered upon discussion with the Sponsor (e.g. ≥ 250 ng of DNA may be sent instead of tissue samples).
5. Patients must have received at least one line of prior systemic therapy for the treatment of MM. A line of treatment is sequential treatment without interruption for response and subsequent progression
6. Patients treated with local radiotherapy (with or without concomitant exposure to steroids for pain control or management of cord/nerve root compression); two weeks must have elapsed since the last date of radiotherapy, which is recommended to be a limited field. Patients who require concurrent radiotherapy should have entry into the Study deferred until the radiotherapy is completed and two weeks have passed since the last date of therapy
7. Patients must have relapsed and/or refractory MM with measurable disease, defined as disease that can be measured either by serum or urinary evaluation of the monoclonal component or by serum assay of free light chain (FLC) of at least one of the following three parameters:
 - Serum M-protein $> 0.5 \text{ g/dL}$
 - Urine M-protein $> 200 \text{ mg per 24 hours}$
 - Involved FLC level $> 10 \text{ mg/dL} (> 100 \text{ mg/L})$ provided serum FLC ratio is abnormal
8. Adequate hematologic function as defined by the following laboratory values performed within 7 days prior to the first dose of vemurafenib:
 - Absolute neutrophil count (ANC) $\geq 1.0 \times 10^9/L$
 - Platelets count $\geq 50 \times 10^9/L$

For all patients (solid tumours and MM):

9. Signed written informed consent approved by the relevant Independent Ethics Committee (IEC) / Institutional Review Board (IRB) must be obtained prior to performing any study-related procedures
10. Male or female ≥ 16 years of age
11. Eastern Cooperative Oncology Group (ECOG) performance status (PS) of 0–2
12. Must have recovered from all side effects of their most recent systemic or local treatment
13. Able to swallow pills
14. Adequate hematologic, renal and liver function as defined by the following laboratory values; tests performed within 7 days prior to the first dose of vemurafenib:

- Haemoglobin \geq 9 g/dL
 - Serum creatinine \leq 1.5 times upper limit of normal (ULN) or creatinine clearance (CrCl) $>$ 50 mL/min by Cockroft–Gault formula (Protocol [Appendix 1](#))
 - Aspartate aminotransferase (AST [SGOT]) and alanine aminotransferase (ALT [SGPT]) \leq 2.5 times ULN (\leq 5 times ULN if considered due to primary or metastatic liver involvement)
 - Serum bilirubin \leq 1.5 times ULN
 - Alkaline phosphatase \leq 2.5 times ULN (\leq 5 times ULN if considered due to tumour)
15. Negative serum pregnancy test within 7 days prior to commencement of dosing in premenopausal women. Women of non-childbearing potential may be included without serum pregnancy test if they are either surgically sterile or have been postmenopausal for \geq 1 year
16. Fertile men and women must use an effective method of contraception during treatment and for at least 6 months after completion of treatment as directed by their physician. Effective methods of contraception are defined as those which result in a low failure rate (i.e., less than 1% per year) when used consistently and correctly (for example implants, injectables, combined oral contraception or intra-uterine devices). At the discretion of the Investigator, acceptable methods of contraception may include total abstinence in cases where the lifestyle of the patient ensures compliance. (Periodic abstinence [e.g., calendar, ovulation, symptothermal, postovulation methods] and withdrawal are not acceptable methods of contraception).
17. Absence of any psychological, familial, sociological, or geographical conditions potentially hampering compliance with the study protocol and follow-up schedule; those conditions should be discussed with the patient before trial entry

*For prostate cancer, ECD and/or LCH specific eligibility criteria as part of Cohort 7, see [Appendix 9](#) and [Appendix 10](#), respectively.

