6.2.1 Dose Modifications, Interruptions, and Delays for Vemurafenib

Management of symptomatic adverse drug reactions (e.g., arthralgia, fatigue, rash) may require temporary interruption and/or dose reduction of vemurafenib treatment. When needed, dose reduction in 240-mg b.i.d. increments is recommended based on individual safety and tolerability. Up to two dose reductions of vemurafenib will be allowed, i.e., to 720 mg p.o. b.i.d., and then to 480 mg p.o. b.i.d. There will be no dosage reductions or interruptions for skin cancer.

Dose escalation after dose reduction is generally not recommended unless under special circumstances, i.e., increased likelihood of clinical benefit for the dose increase and no safety concerns. This should only be done after discussion with the Sponsor. Dose increases above 960 mg b.i.d. are NOT allowed.

Patients with ECD/LCH have the option of discontinuing vemurafenib treatment after one year, if the investigator considers it to be in the best interest of the patient. Patients can then resume vemurafenib treatment if they become symptomatic or if their scans show worsening of their disease.

Dosage modification criteria should occur as follows (also see Table 11):

**Table 11:
Dose Interruption/Modification Criteria for Vemurafenib**

Toxicity Grade (CTCAE, v4.0) ^a	Vemurafenib dose changes during current treatment period	Dose adjustments for resumption of treatment
Grade 1	100% of starting dosage	100% of starting dosage
Tolerable Grade 2	100% of starting dosage	100% of starting dosage
Intolerable Grade 2		
First appearance	Interrupt until resolved to Grade 0 – 1	Reduce by 240 mg b.i.d.
Second appearance	Interrupt until resolved to Grade 0 – 1	Reduce by 240 mg b.i.d.

Toxicity Grade (CTCAE, v4.0) ^a	Vemurafenib dose changes during current treatment period	Dose adjustments for resumption of treatment
Third appearance	Discontinue permanently	
Grade 3 ^b		
First appearance	Interrupt until resolved to Grade 0 – 1	Reduce by 240 mg b.i.d.
Second appearance	Interrupt until resolved to Grade 0 – 1	Reduce by 240 mg b.i.d.
Third appearance	Discontinue permanently	–
Grade 4		
First appearance	Discontinue permanently or interrupt until resolved to Grade 0 – 1 ^c	Reduce to 50% of starting dosage or reduce to 480 mg b.i.d. if starting dose is 720 mg b.i.d.
Second appearance	Discontinue permanently	–

a. Common Terminology Criteria for Adverse Events, Version 4.0.

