b. Treatment interruptions or and/or dose reductions for Grade 3 haematology test abnormalities, except for neutropenia and thrombocytopenia, will be at investigator's discretion.

c. Discontinue permanently if starting dose is 480 mg b.i.d.

Prolongation of the corrected QT (QTc) interval (change from baseline) was observed in a substudy of the NP22657/BRIM-2 phase II trial. As a result of these findings, the following recommendations have been developed to minimize the risk of ventricular arrhythmia in patients with metastatic melanoma treated with vemurafenib:

Avoid combination with other agents with known potential to lead to prolongation of QTc interval, if possible.

ECG monitoring, with a focus on QTc interval, should occur during the Screening/Baseline period, 28 days after starting vemurafenib, every 28 days for the following 3 months, and every 12 weeks thereafter until study drug discontinuation at the End of Treatment Visit, and at the Safety Follow-Up Visit.

If QTc interval exceeds 500 ms or the change from baseline is > 60 ms, vemurafenib treatment should be temporarily interrupted. The Investigator should check electrolytes (K+, Mg++, and Ca++) with a focus on hypokalaemia, correct any electrolyte abnormalities prior to reinstitution of therapy, recheck concomitant medications to insure that none has been implicated in QTc prolongation, and rule out or control other cardiac risk factors (i.e., ischemia). ECG should be monitored weekly until QTc decreases to less than 500 ms, at which point treatment should be reinitiated at one reduced dose level, i.e., from 960 mg b.i.d. to 720 mg b.i.d. If a subsequent increase in QTc to > 500 ms or change from baseline is > 60 ms is observed, vemurafenib may be reduced to 480 mg b.i.d.

Vemurafenib should be permanently discontinued if a QTc increase meets both criteria of > 500 ms and > 60 ms change from pre-treatment values or if QTc > 500 ms or change from baseline > 60 ms is observed on two separate prior occasions.

If a patient's study dose has been interrupted for > 4 weeks due to an AE the patient will be considered to have discontinued from the study. However, a temporary discontinuation of drug

for up to 4 weeks is allowed in case of tumour surgery or other procedures for safety reasons or in the best patient interest, or elective procedures in the best patient interest.

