6.3.2.2 Dose-limiting toxicities (Cohort 3b only)

DLT is defined as a clinically significant adverse event or abnormal laboratory value assessed as unrelated to disease progression, undercurrent illness, or concomitant medications and occurring during the first 4 weeks of treatment with the combination of vemurafenib and cetuximab.

For the purposes of this protocol, the following adverse events determined to be possibly, probably or definitely related to the combination of cetuximab and vemurafenib that occur during the 28 days following the first administration of the combination of vemurafenib and cetuximab at any dose level and that meet any of the following criteria are considered to be dose-limiting toxicities (DLT) that count for the determination of the MTD.

Toxicity grades are defined in the NCI CTCAE v 4.0 ([80](#)).

- Grade ≥ 3 non-haematological toxicity (other than untreated nausea, vomiting and diarrhoea and excluding alopecia)
- Grade ≥ 3 nausea, vomiting or diarrhoea refractory to appropriate treatment for at least 2 days
- Grade 4 anaemia lasting > 7 consecutive days
- Neutropenia Grade 4 lasting > 7 consecutive days
- Neutropenia Grade 3 or 4 complicated by fever and/or infection (ANC $<1.0 \times 10^9/L$; fever $\geq 38.5^\circ C$)
- Grade 4 thrombocytopenia lasting > 7 consecutive days
- Treatment delay >33% of the scheduled doses over 28 days due to treatment related toxicity

Skin and subcutaneous tissue toxicity is not considered a DLT unless a dose reduction of study treatment is required to permit continuous dosing.

6.3.3 Dose Modifications, Interruptions, and Delays for Vemurafenib and Cetuximab (Cohort 3b only)

For all patients in Cohort 3b when an occurring toxicity can be clearly ascribed to either cetuximab or vemurafenib, it will be considered to only dose reduce the compound responsible for the toxicity. See [Table 13](#) for the recommended cetuximab dose interruptions/ modifications and [Section 6.2.1](#) for vemurafenib dose reductions.

When an occurring toxicity cannot be clearly ascribed to either cetuximab or vemurafenib, both drugs will be dose reduced as per guidance in [Table 11](#) and [Table 13](#) for vemurafenib and cetuximab respectively.

Table 13:
Dose Interruption/Modification Criteria for Cetuximab

Toxicity Grade (CTCAE, v4.0) ^a	Cetuximab dose changes during current treatment period	Dose adjustments for resumption of treatment of weekly dose

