8. STATISTICAL CONSIDERATIONS AND ANALYTICAL PLAN

8.1 PRIMARY AND SECONDARY STUDY VARIABLES

8.1.1 Primary Variable

Response rate at Week 8, as assessed by the Investigator using RECIST, v1.1* for patients with solid tumours or IMWG uniform response criteria for patients with MM, is the primary endpoint for each cohort. For patients with solid tumours, responders at Week 8 will be defined based on tumour assessment status of PR or CR at Week 8. For patients with MM, responders at Week 8 will be defined based on tumour assessment status of CR, sCR, VGPR or PR. Only patients with measurable disease at baseline will be included in the analysis of the RR. Patients without a post-baseline tumour assessment will be considered to be non-responders.

There will be 7 cohorts with different cancer types. There will be Cohort 3a and 3b with patients with colorectal cancer treated with vemurafenib or vemurafenib in combination with cetuximab, respectively.

Cohort 3b has two parts,

Part 1 is a dose finding phase for vemurafenib in combination with cetuximab (based on a classical 3+3 design)

Part 2 is investigating the efficacy and safety of the recommended dose for stage I/II of the combination of vemurafenib and cetuximab

*see [Appendix 9](#) for prostate cancer, [Appendix 10](#) for ECD and/or LCH response criteria

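### A myeloma patient who enters near the ANC limit, dips below it and recovers to the entry count cannot resume vemurafenib under Table 11, and after 4 weeks counts as discontinued

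*Protocol*

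**What the plan says.** **Entry.** Protocol Section 4.2, criterion 8 (myeloma only), accepts "Absolute neutrophil count (ANC) $\geq 1.0 \times 10^9/L". Criterion 3, for solid tumours, requires "Absolute neutrophil count (ANC) $\geq 1.5 \times 10^9/L". The lower limit is specific to Cohort 6.

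**Grade.** The protocol prints no CTCAE grade table. Section 6.3.2.2, in the dose-limiting toxicity list for Cohort 3b, includes "Neutropenia Grade 3 or 4 complicated by fever and/or infection (ANC $<1.0 \times 10^9/L". That section and Table 11 both use CTCAE v4.0.

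**Interruption and resumption.** For a first or second Grade 3 event, the entry in Table 11 (Section 6.2.1) begins "Interrupt until resolved to Grade 0"; the range given there ends at Grade 1, and a dose reduction follows. For tolerable Grade 2 it keeps the full starting dose. Footnote b gives the investigator discretion, but with two exceptions ("for Grade 3 haematology test abnormalities, except for neutropenia and thrombocytopenia, will be at"), so Grade 3 neutropenia follows the table.

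**Time limit.** Section 6.2.1 adds a consequence for long interruptions: "study dose has been interrupted for > 4 weeks due to an AE the patient will be considered to have discontinued from the study".

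**Follow-up of adverse events.** For related events, Section 7.2.2 accepts return to the baseline state as an end point of follow-up. Table 11 has no such clause.

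**Schedule.** Haematology is checked on Days 1, 15 and 29 and then every 28 days. The first on-treatment myeloma assessment is at 8 weeks (Section 5.3.2).

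**The concern.** The entry rule admits patients right at the border of Grade 3. The resumption rule then asks for a count better than the one at which they were enrolled. Under Table 11, a count acceptable for starting at full dose, and for continuing at full dose as tolerable Grade 2, is not acceptable for resuming at a reduced dose. A patient whose counts are low because of marrow disease could recover completely to the pre-treatment value and still be unable to restart.

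At stake is whether some Cohort 6 patients leave treatment because of how two rules meet rather than because of toxicity beyond their starting state. Stage I has only seven patients, so a single such case can matter for the decision to continue the cohort.

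**Working it through.** **1. The chain, rule by rule**

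- Entry ANC is 1.0 × 10^9/L or just above (criterion 8).
- Section 6.3.2.2 associates ANC below 1.0 with Grade 3 or 4 neutropenia. A patient at 1.0 is at the lower edge of Grade 2, so is not at Grade 0–1. The value separating Grade 1 from Grade 2 is not printed and is not needed for this step. It would be needed to say how far above 1.0 the affected range extends.
- A fall below 1.0 is Grade 3. Interruption is mandatory (Table 11, footnote b).
- Recovery to the entry count is recovery to Grade 2. Table 11 requires Grade 0–1, so the drug stays off.
- A laboratory value that leads to interruption is recorded as an adverse event (Section 7.2.3). The 4-week rule for interruptions due to an adverse event therefore applies.

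**2. Timeline**

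An interruption starting on Day d first exceeds 28 days on Day d + 29. Compare this with the nominal Week 8 visit on Day 57.

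| Fall found on | More than 4 weeks on | Before Day 57? |
|---|---|---|
| Day 13 (15 − 2) | Day 42 | yes |
| Day 15 | Day 44 | yes |
| Day 17 (15 + 2) | Day 46 | yes |
| Day 24 (29 − 5) | Day 53 | yes |
| Day 29 | Day 58 | no |
| Day 34 (29 + 5) | Day 63 | no |

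Discontinuation before Week 8 needs d + 29 < 57, that is d ≤ 27. In practice this means the Day 15 check, an early Day 29 visit or an unscheduled test. A fall found on Day 29 leaves the patient on study at Day 57, but assessed after 28 days off drug.

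**3. The plan's own figures**

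The rule in Table 16 (Section 8.4) is: with 0–1 of 7, stop; with 2–4 of 7, go to 19 and require at least 5; with 5–7 of 7, go to 13 and require at least 6. With b(x; 7, p) the binomial probability:

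P(positive) = Σ(x = 2 to 4) b(x; 7, p) · P(Bin(12, p) ≥ 5 − x) + Σ(x = 5 to 7) b(x; 7, p) · P(Bin(6, p) ≥ max(0, 6 − x))

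- p = 0.15: 0.0990 + 0.0008 = 0.0998 (plan: alpha 10%)
- p = 0.35: 0.6532 + 0.0521 = 0.7053 (plan: power 70%)
- p = 0.45: 0.7330 + 0.1497 = 0.8827 (plan: power 80%, met as a minimum)

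The enumeration agrees with the table.

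**4. Effect of one forced non-responder on Stage I**

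The responder threshold is missed with 0 or 1 responder. With n patients able to respond, P(stop) = (1 − p)^n + n·p·(1 − p)^(n − 1).

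- p = 0.35, n = 7: 0.0490 + 0.1848 = 0.2338
- p = 0.35, n = 6: 0.0754 + 0.2437 = 0.3191
- p = 0.45, n = 7: 0.0152 + 0.0872 = 0.1024
- p = 0.45, n = 6: 0.0277 + 0.1359 = 0.1636

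One patient who cannot count as a responder raises the chance of missing the threshold from 23.4% to 31.9% at a true rate of 35%, and from 10.2% to 16.4% at 45%. These figures are conditional on one such patient occurring. They do not say how likely that is.

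**The case against.** **The two rules do not conflict in the literal sense.** An entry limit and a resumption limit serve different purposes, and a site can follow both. That stands. The point is narrower: followed literally, they keep off treatment a patient who has returned to the state in which the plan chose to enrol them, and Table 11 does not show that this was considered.

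**The grade anchor is indirect.** The 1.0 value sits in a Cohort 3b toxicity item about neutropenia with fever or infection, not in a grade table. True, but it is the protocol's own association of a count with Grade 3 or 4, under the same CTCAE version as Table 11.

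**The event may be rare.** Section 1.3.5 describes neutropenia as uncommon (0.6%), typically arising in the first 6–12 weeks, usually reversible within 2 weeks, and in some cases managed with G-CSF. This limits the weight considerably. It does not remove the point, because the description is not specific to patients with low counts at entry, for whom reversal to baseline is not enough.

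**The illustration is not the full decision rule.** The title of Table 16 excludes Cohort 6, although its body says all cohorts and Table 15 lists myeloma with 19 and 13 patients. Section 8.3.1.2 also allows a cohort to continue on clinical benefit, and at Stage II offers a confirmed-BOR route. The Stage I figures are therefore illustrative only.

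**Counting early withdrawal against the drug is intended.** Section 8.3.1 includes patients who withdraw prematurely from study medication in Stage I. That is a fair design choice. It does not bear on whether the withdrawal itself should follow from a resumption rule set above the entry level.

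**A reader might infer that such a patient automatically becomes a non-responder,** because Section 8.1.1 says "Patients without a post-baseline tumour assessment will be considered to be non-responders". The documents do not support that. The End of Treatment visit includes a myeloma assessment if none was done in the last 28 days (Section 5.3.3), so a post-baseline assessment may exist. The protocol does not say whether it counts for Week 8, and Section 5.3.6.2 asks for two consecutive assessments.

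**Conclusion.** The mismatch is in the text. For a Cohort 6 patient enrolled near ANC 1.0, recovery to the entry count after a Grade 3 fall does not permit resumption, and after more than 4 weeks the patient is considered discontinued. This precedes Week 8 only if the interruption starts by Day 27. The point is modest: worth settling at the next amendment, but not shown to bias the cohort result by any known amount.

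The 23.4% to 31.9% figure assumes a true response rate of 35%, exactly one forced non-responder among the first seven, and the Table 16 threshold applied to myeloma without the clinical-benefit route.

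Two further readings are tempting and not supported. A reader might infer a loss of power for the whole cohort. The protocol gives neither the share of patients entering near the limit nor the share who would fail to reach Grade 0–1, so any such figure would rest on an invented fraction. A reader might also extend the point to the myeloma platelet limit ("Platelets count $\geq 50 \times 10^9/L") or to the wider liver limits of criterion 14. The protocol prints no grade limits for either, so the documents alone cannot show the same mismatch there.

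**What to change.** Reconcile three places for patients enrolled within the myeloma ANC limit: criterion 8 in Section 4.2, Table 11 with footnote b, and the 4-week rule in Section 6.2.1. After the change it should be clear what happens to a patient whose count returns to its entry value but not to Grade 0–1. Which passage changes, and to what, is a clinical decision for the sponsor's clinical team, and none is proposed here.

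The cost is a short clarification in the next amendment, with no extra patients, visits or tests.
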